## **Privacy & Data Security**

Study data will require the use of identifiers only as long as necessary data collection is on-going. Data storage will occur only on encrypted desktop computers in the Center for Hip and Knee Replacement (PH1155) and the multi-user system ID #6692 that has been approved as a certified environment by Columbia. As soon as the required study information is collected, the patient names and MRNs will be replaced with patient numbers (patient 1,2,3,4.....). The only document linking study codes to patients will be protected by a password and safely stored on an encrypted desktop computer in a locked CUMC office as well as on the multi-user system ID #6692 that has been approved as a certified environment by Columbia.

Subjects will only be consented in private office rooms with only necessary research personnel. Research personnel and medical staff will be reminded to not discuss study participation outside closed private offices with study participants and research personnel.

## **Study Procedures**

Patients undergoing TKA will be randomized to receive OrthoSeonsor or surgeon-guided ligamentous balancing. Patient-reported outcomes, pain levels, range of motion will be assessed at 3 month, 6 month, 1 year, and 2 year follow up visits.

No new pre, intra, or post-operation procedures will take place if you choose to take part in this study.

Before surgery, as we do with other non-study patients, you will be asked to complete several questionnaires to evaluate the function of your knee. Also as per standard of care, your knee will be evaluated by a few brief physical exams (i.e. range of motion tests, leg stability tests, neurovascular exam).

On the day of your surgery, your TKA will be performed either with or without utilization of the OrthoSensor device. This is to be decided randomly.

As a follow-up schedule, you will be seen at three months post-operation, six months post-operation, one year post-operation, and two years post-operation, where you will repeat the standard questionnaires. You will repeat the standard physical therapy exams. These visits will include the standard of care post-operative practices, exams and questionnaires.

The information recorded at the physical exams and on the questionnaires will be viewed and used by the study team to evaluate the procedure.

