## **Study Design**

In a randomized-controlled fashion, this investigation will evaluate the use of the Verasense technology to achieve optimal TKA balance. Patients will be randomized to either: 1) undergo manual soft tissue balancing or 2) soft tissue balancing with the Verasense. The primary outcomes of interest will include patient-reported outcomes as well knee range of motion at 3 months, 6 months, 1 year, and 2 years. Secondary outcomes of interest will include pain level as assessed by the visual analogue scale (VAS) in the acute post-operative and follow up periods, ambulation distance during inpatient physical therapy postoperatively, surgical time, tourniquet time, amount of opioid consumption, length of hospital stay, incidence of arthrofibrosis and subsequent manipulation under anesthesia. We hypothesize that the use of the Verasense technology will lead to improved soft tissue balancing in TKA and ultimately result in favorable patient-reported outcomes and postoperative knee range of motion.

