### **Study Devices**

Device name: VERASENSE knee system

Device description: The device is a computer assistance device that is temporarily inserted into the tibial tray during total knee replacement. The device measures pressures and alignment in the knee intraoperatively.

Device Model/Version #: K130380

Phase of Study: Pivotal

Manufacturer Information: OrthoSensor

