### **Recruitment and Consent**

Subjects will be voluntarily recruited from the Principal Investigator or Sub-Investigator clinic population and/or referring physicians. Subjects who present with osteoarthritis or degenerative bone disease will be screened to determine if they meet all inclusion and no exclusion criteria. If all entry criteria are achieved, the subject will be eligible to participate in the study. All general and indication-specific entry criteria must be met prior to study entry. All relevant medical and non-medical conditions will be taken into consideration when determining whether a patient is suitable for participation within the study. As potential subjects will be under the clinical care of the study investigators, subjects will initially be informed of the study by each of the treating physicians. Researchers will not approach a patient for recruitment until that patient is informed of the study by the physician or PI on this study and the PI has ascertained that the patient is willing to discuss the study with the investigators. The sponsor is providing the devices in the same manner they currently provide them in the hospital.

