#### **Risks, Benefits and Monitoring**

Loss of confidentiality is a potential risk. There are no other known risks for participating in this study beyond those described by the physician as part of the standard of care TKA procedure.

The potential benefits of this study include improved soft-tissue balancing and improved rotational congruency between the medial and lateral compartments in the knee undergoing operation. Another is improving the orthopaedic field's understanding of how medial and lateral compartment pressures, as well as rotational alignment, correlate with patient outcome. A final potential benefit is improving the standard of care for TKA, if the OrthoSensor™ device proves to be a reliable enhancer of patient outcomes and success rate.

Patients who are eligible for TKA, but do not wish to participate in the trial can decline participation and receive the treatment modality of their choice.

Patient confidentiality will be maintained through the storage of study data on encrypted, password protected devices, accessible only to approved study personnel. All non-digital information will be stored in a locked file cabinet available only to the principal investigator and key approved personnel. In the unlikely event that some potentially harmful consequence of the study occurs, medical and other professional intervention will be available and provided for the patient. Each patient enrolled will be given a study ID number, which will be used for the duration of the study instead of patient information. The match list with the study identifiers will be stored on a local, encrypted, password protected drive only to be available to key study personnel.

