#### **Study Subjects**

Participation Duration: 2 years

Anticipated Number of Subjects: 130

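### The primary outcomes are self-rated or measured by an examiner, yet the visible plan has no step to keep patients or range-of-motion examiners unaware of the arm

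*Combined protocol and SAP*

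**What the plan says.** Study Design sets the endpoints: "The primary outcomes of interest will include patient-reported outcomes as well knee range of motion", at 3 months, 6 months, 1 year and 2 years. It also states the hypothesis that the sensor will give favourable results on both. Study Procedures repeats the timing: "Patient-reported outcomes, pain levels, range of motion will be assessed at 3 month, 6 month, 1 year, and 2 year follow up visits".

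On how the data arise, Study Procedures says that patients complete questionnaires and have physical examinations at each visit: "You will repeat the standard physical therapy exams". It does not say who measures range of motion.

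On the difference between arms, Study Procedures says only that the operation is done with or without the device, decided at random. Study Devices describes the sensor as "temporarily inserted into the tibial tray during total knee replacement". A single visit schedule, beginning "As a follow-up schedule, you will be seen at three months post-operation", is given without distinction by arm.

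Neither section says whether patients or examiners know the arm, and neither declares the trial open-label.

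**The concern.** A patient who knows that a sensor guided the operation may rate pain and function differently from one who knows that it did not. An examiner who knows the arm may read a range-of-motion measurement differently. Both types of primary outcome are therefore exposed. Randomisation balances the arms at entry, but it does not remove bias that arises afterwards from knowledge of the arm.

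The likely direction is not neutral. Study Design hypothesises a benefit, and the Lay Abstract contrasts measured pressure readings with reliance on the surgeon's judgement. The t-test and Fisher exact test named under Statistical Procedures cannot separate an effect of balancing from an effect of expectation or observation.

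Timing matters too. Masking has to be arranged before surgery and cannot be added at analysis.

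**Working it through.** There is no figure in the plan to reproduce on this point, so the main check is a reading of the visible text.

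**Is masking covered anywhere?**
- Study Design and Study Procedures give randomisation, outcomes and timing. They contain no statement about knowledge of the arm.
- Statistical Procedures names tests only.
- Privacy & Data Security and Risks, Benefits and Monitoring replace names with study numbers and restrict where participation is discussed. These measures protect identity; they do not hide the arm from the patient or the examiner.

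**Could patients be masked?**
- For: the sensor does not stay in the knee (Study Devices), and the described follow-up is the same for everyone (Study Procedures). Neither the implant nor the visits need reveal the arm.
- Against: the device is already in use at the hospital, "The sponsor is providing the devices in the same manner they currently provide them in the hospital", and eligible patients who do not want to join "can decline participation and receive the treatment modality of their choice". The second statement concerns non-participants, but together they suggest that some participants may know of the device and ask.

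**Could examiners be masked?** The operating surgeon cannot be. Recruitment and Consent places patients under the investigators' clinical care, so the surgeon may also be the examiner. The visible text does not settle this.

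**Illustration of scale.** The one input from the plan is "Anticipated Number of Subjects: 130". Everything else is assumed: 1:1 allocation (130 / 2 = 65 per arm), two-sided 0.05, one normally distributed score compared by t-test, no true effect, and a bias of b SD entered as a mean shift. For the second column, an assumed 20% loss gives 65 × 0.8 = 52 per arm.

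The rejection probability comes from the noncentral t distribution with 2n − 2 degrees of freedom and noncentrality b / √(2/n):
- n = 65: √(2/65) = 0.1754, so b = 0.1, 0.2, 0.3 gives noncentrality 0.570, 1.140, 1.710, with 128 degrees of freedom.
- n = 52: √(2/52) = 0.1961, so noncentrality is 0.510, 1.020, 1.530, with 102 degrees of freedom.

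| Assumed bias | 65 per arm | 52 per arm |
|---|---|---|
| none | 5% | 5% |
| 0.1 SD | 8.7% | 8.0% |
| 0.2 SD | 20.5% | 17.3% |
| 0.3 SD | 39.7% | 32.9% |

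These percentages would apply to any two-arm t-test of this size. They say nothing about how large the bias would be in this trial.

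**The case against.** The strongest reply is that this is a claim of absence made on incomplete text. Title and consent pages, among others, were not available. Study Procedures is partly written to the patient, so a consent form may say more about what patients are told. A reader might infer from the silence that the trial is open-label; the documents do not support that, because no visible text says so. What remains is narrower: a masking step would be expected in Study Design or Study Procedures, both can be read, and neither contains one.

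A second reply is that feasibility is inferred. For patients the inference has support in the text. For examiners it does not, since nobody is named as measuring range of motion. It would be wrong to conclude that examiner masking is simply available, and that part of the request has to be conditional.

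A third is that keeping the arm from patients for two years, while their treating surgeons know it, is a working rule and not just a sentence in the protocol. That stands and belongs in the cost.

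A fourth is that the percentages rest wholly on assumed inputs. That also stands. A reader might take them as the false-positive rate of this trial, but the documents give no bias size, allocation ratio, significance level or loss rate to support such a reading.

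**Conclusion.** The concern holds in a limited form. As visibly written, the plan includes no step to keep patients or range-of-motion examiners unaware of the arm, although both types of primary outcome can be influenced by that knowledge. A difference favouring the sensor would be open to an explanation by expectation or observer effects. It is not shown that the trial is in fact unmasked, or that any bias would occur.

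The size of the problem cannot be derived from the documents, and the illustrative percentages carry no weight in this conclusion. It rests on three things: the choice of primary outcomes, the absence of a masking step in the sections where one would be expected, and the apparent feasibility of masking patients. It should be addressed, with medium confidence given the pages that could not be checked.

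**What to change.** Add to Study Design and Study Procedures that patients are not told their arm until their 2-year assessments are complete, and bring the consent wording into line. If such a rule already exists on a page not seen here, repeat it in these two sections.

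For range of motion, state who measures it. Where existing clinic or physical-therapy staff other than the operating surgeon already do so, have them measure without access to the operative note or the allocation. No new staff are requested. Where the surgeon is the examiner, interpret range of motion as unmasked and word the conclusion accordingly.

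Merely declaring the trial open-label would make the report honest but would leave the self-rated outcomes as exposed as before, so it is second best.

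Cost: protocol and consent wording, plus a continuing rule for surgeons and clinic staff on not disclosing the arm; no new visits or assessments. Masking will be imperfect, because surgeons know the arm and some patients may ask or see their records.

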### **Study Devices**

Device name: VERASENSE knee system

Device description: The device is a computer assistance device that is temporarily inserted into the tibial tray during total knee replacement. The device measures pressures and alignment in the knee intraoperatively.

Device Model/Version #: K130380

Phase of Study: Pivotal

Manufacturer Information: OrthoSensor

### **Recruitment and Consent**

Subjects will be voluntarily recruited from the Principal Investigator or Sub-Investigator clinic population and/or referring physicians. Subjects who present with osteoarthritis or degenerative bone disease will be screened to determine if they meet all inclusion and no exclusion criteria. If all entry criteria are achieved, the subject will be eligible to participate in the study. All general and indication-specific entry criteria must be met prior to study entry. All relevant medical and non-medical conditions will be taken into consideration when determining whether a patient is suitable for participation within the study. As potential subjects will be under the clinical care of the study investigators, subjects will initially be informed of the study by each of the treating physicians. Researchers will not approach a patient for recruitment until that patient is informed of the study by the physician or PI on this study and the PI has ascertained that the patient is willing to discuss the study with the investigators. The sponsor is providing the devices in the same manner they currently provide them in the hospital.

### **Research Aims and Abstracts**

Research Purpose:

The purpose of this study is to find out whether using a device to measure pressure inside a replacement knee can help the replacement knee work better long term.

Research Question(s)/Hypothesis(es):

Utilization of the OrthoSensor system will provide improved gap balancing and functional outcomes

Scientific Abstract:

It is thought that inter-compartmental soft tissue balance is an important factor with regards to primary TKA success rate. Until recently however, there has not been a way of quantifying this balance to rigorously check the validity of this correlation and determine whether ligamentous balancing

quantification improves surgical and patient-reported outcomes. Consenting patients (n=130) who present with an arthritic knee indicative of primary TKA will be randomized to undergo TKA either utilizing the OrthoSensor tibial trial device, which provides intra-operative compartmental pressure readings, or via the analogous standard of care TKA without the OrthoSensor device. Both groups will be evaluated both pre and post-operatively with various knee use scores (KSFS, WOMAC, and SF 12). The data will be analyzed to evaluate the efficacy of the OrthoSensor device and its effects on early clinical outcomes.

#### Lay Abstract:

In total knee replacements, it is thought that the tension on the medial compartment of the knee must be in balance with the tension on the lateral compartment of the knee for the replacement to work well and last. Until recently however, there has not been a way to test this claim with hard numbers. In this study, patients who have an arthritic knee, and are recommended to undergo total knee replacement surgery will either receive surgery using the OrthoSensor device, which provides real-time pressure readings on the compartments, or via the standard of care for total knee replacement, a procedure that solely relied on the surgeons experience and feel to balance the two compartments. By collecting quality of life, pain, and knee function information before and after surgery (at multiple post-surgery visits), efficacy of the OrthoSensor device and its effect on patients outcome will be compared.

#### **Risks, Benefits and Monitoring**

Loss of confidentiality is a potential risk. There are no other known risks for participating in this study beyond those described by the physician as part of the standard of care TKA procedure.

The potential benefits of this study include improved soft-tissue balancing and improved rotational congruency between the medial and lateral compartments in the knee undergoing operation. Another is improving the orthopaedic field's understanding of how medial and lateral compartment pressures, as well as rotational alignment, correlate with patient outcome. A final potential benefit is improving the standard of care for TKA, if the OrthoSensor™ device proves to be a reliable enhancer of patient outcomes and success rate.

Patients who are eligible for TKA, but do not wish to participate in the trial can decline participation and receive the treatment modality of their choice.

Patient confidentiality will be maintained through the storage of study data on encrypted, password protected devices, accessible only to approved study personnel. All non-digital information will be stored in a locked file cabinet available only to the principal investigator and key approved personnel. In the unlikely event that some potentially harmful consequence of the study occurs, medical and other professional intervention will be available and provided for the patient. Each patient enrolled will be given a study ID number, which will be used for the duration of the study instead of patient information. The match list with the study identifiers will be stored on a local, encrypted, password protected drive only to be available to key study personnel.

#### **Study Subjects**

Participation Duration: 2 years

Anticipated Number of Subjects: 130
